NON-INTERVENTIONAL (NI) STUDY PROTOCOL

This document contains confidential information belonging to Pfizer. Except as otherwise agreed to in writing, by accepting or reviewing this document, you agree to hold this information in confidence and not copy or disclose it to others (except where required by applicable law) or use it for unauthorized purposes. In the event of any actual or suspected breach of this obligation, Pfizer must be promptly notified.

Study Information

Title	BASELINE VARIABLES PREDICTING TREATMENT RESPONSE AT 6 MONTHS IN ADULT RHEUMATOID ARTHRITIS PATIENTS TREATED WITH TOFACITINIB 5MG BID IN A NON-INTERVENTIONAL SETTING (TREAT-RA)
Protocol number	A3921342
Protocol version identifier	2.0
Date	14 January 2020
Active substance	L04AA29 tofacitinib
Medicinal product	Xeljanz
Research question and objectives	The primary objective of this non-interventional study is to identify baseline characteristics of patients that predict response at 6 months of treatment. The study also aims to describe the treatment patterns of RA patients prescribed tofacitinib in a real-world setting and assess the effect of treatment on patient quality of life and physical function. Finally the study will assess the use of healthcare resources and costs in patients with RA treated with tofacitinib in Greece.
Author	PPD [REDACTED] MD, MSc PPD [REDACTED] PPD [REDACTED] [REDACTED]

2. LIST OF ABBREVIATIONS

Table 1. List of Abbreviations

Abbreviation	Definition
ACR	American Colleague of Rheumatology
AE	Adverse Event
AEM	Adverse event monitoring
ALT	Alanine transaminase
AST	Aspartate transaminase
CCP	Cyclic citrullinated protein
DCT	Data Capture Tool
CDAI	Clinical Disease Activity Index
CIOMS	Council for International Organizations of Medical Sciences
DCTDCT	Data Collection Tool
CRP	C-reactive Protein
CSR	Clinical Study Report
DAS	Disease Activity Score
DMARD	Disease Modifying Antirheumatic Drugs
EDP	Exposure during pregnancy
EIU	Exposure in Utero
EMA	European Medicines Agency
ENCePP	European Network of Centres for Pharmacoepidemiology and Pharmacovigilance
EQ-5D	EuroQol five dimensions questionnaire
ESR	Erythrocyte sedimentation rate
EULAR	European League Against Rheumatism
FACIT	Functional Assessment of Chronic Illness Therapy
FDAAA	Food and Drug Administration Amendments Act
GCP	Good Clinical Practice
GEP	Good Epidemiological Practice
GGT	Gamma-glutamyl transferase
GPP	Good Pharmacoepidemiology Practices
HAQ-DI	Health Assessment Questionnaire – Disability Index
HDL	High-density lipoprotein,
IEA	International Epidemiological Association
IEC	Independent Ethics Committee
IL	Interleukin
INF	Interferon
INR	International normalized ratio
IRB	Institutional Review Board
ISPE	International Society for Pharmacoepidemiology
ISPOR	International Society for Pharmacoeconomics and Outcomes Research

Abbreviation	Definition
JAK	Janus kinase
LDL	Low-density lipoprotein,
LFT	Liver function test
LSLV	Last subject, last visit
MCP	Metacarpophalangeal joint
MTX	Methotrexate
NI	Non-Interventional
NSAID	Nonsteroidal Anti-Inflammatory Drugs
PASS	Post-Authorization Safety Study
PCD	Primary Completion Date
PhRMA	Pharmaceutical Research and Manufacturers of America
PIP	Proximal interphalangeal joints
PML	Progressive multifocal leukoencephalopathy
PT	Prothrombin time
PY	Patient years
RA	Rheumatoid arthritis
SAE	Serious Adverse Events
SAP	Statistical Analysis Plan
SDAI	Simplified Disease Activity Index
SmPC	Summary of Product Characteristics
SOA	Schedule of activities
SRA	Serum rheumatoid factor
TB	Tuberculosis
TNF	Tumor necrosis factor
TyK	Tyrosine kinase
ULN	Upper limit of normal
VAS	Visual Analogue Scale
WPAI	Work Productivity and Activity Impairment

4. ABSTRACT

N/A.

5. AMENDMENTS AND UPDATES

Table 3. Amendments and Updates

Amendment number	Date	Protocol section(s) changed	Summary of amendment(s)	Reason
1.0	14/01/2020	Title Page, 2	Updated Study Team.	Team Change.
		8.2.1	Clarified Inclusion criterion 3.	Clarifying treatment status at the enrolment.
		8.7.3.4.2	Updated formula for work productivity loss scoring.	Corrected typographical mistake.
		5	Updated Milestones.	Adapted to expected dates.
		Throughout	Updated template.	New Template issued.

6. MILESTONES

Table 4. Milestones

Milestone	Planned date
Completion of feasibility assessment	Oct 2019
Start of data collection	May 2020
End of data collection	May 2022
Final study report	April 2023

7. RATIONALE AND BACKGROUND

Rheumatoid arthritis (RA) is a chronic, autoimmune disease characterized by joint inflammation and destruction, leading to a progressive disability and adverse psychological effects with severe impact on patients' quality of life.¹ Apart from musculoskeletal complications directly related to their rheumatic disease, RA subjects are also at increased risk of suffering from co-morbidities such as cardiovascular and infectious diseases, osteoporosis, depression and cancer, contributing to the higher mortality rate observed in RA patients compared to the general population.²

The chronic nature of the disease deems necessary the long-term use of medication. Thus, RA represents significant health and socioeconomic burdens for the individual subject, healthcare systems and society, with indirect costs (productivity loss, absenteeism/disability, early retirement) accounting for up to ¾ of total costs for working patients.³

As there is currently no cure for RA, the target of treatment strategies is to control disease activity, alleviate signs and symptoms, maintain physical function, optimize quality of life, reduce the rate of joint damage, and, if possible, induce and maintain complete remission.¹ Although there are several effective treatments available nowadays, mainly biologic DMARDs, many patients fail to achieve or maintain the desired response and are treated sequentially with different drugs leading to increased costs, risk of toxicity and suboptimal effectiveness. Therefore, the ambition for personalized treatment has emerged and investigation to identify predictive tools of treatment response is a highly active area of research.⁴

Tofacitinib (CP-690,550) is an oral Janus kinase (JAK) inhibitor that targets inflammation by reducing pro-inflammatory cytokine signaling and production.⁵

The efficacy and safety evaluation of tofacitinib for the treatment of RA is based on a comprehensive clinical development program including six randomized, double blind, multicenter phase III studies in adult subjects with active rheumatoid arthritis (RA). In these trials tofacitinib consistently reduces signs and symptoms of RA, improves physical function and other subject-reported outcomes such as fatigue, pain and health-related aspects of quality of life in subjects with moderate to severe RA. Combined with its inhibition of the progression of structural damage, the development program has demonstrated tofacitinib as an effective targeted synthetic disease-modifying anti-rheumatic drug (DMARD) in treating RA.⁶⁻¹¹ Long-term extension and Phase 3b/4 post authorization safety studies are aimed to demonstrate sustained efficacy and a consistent safety profile as seen in the Phase 2 and 3 controlled clinical trials.

However, these trials may have limitations reflecting real world situations. It has been estimated that only 21-33% of patients documented in registries, reflecting more accurately routine care, would have met eligibility criteria of major trials as they often exclude patients with co-morbidities.¹² Also treatment of patients in daily clinical practice may vary from the strictly regulated schemes followed in clinical trials. Therefore, additional long-term data in registries and non-interventional studies of a European population would be helpful to further assess treatment outcomes in a real-world setting.

PFIZER CONFIDENTIAL

29-Jul-2019 Page 9

Furthermore, studies exploring the association between clinical and biochemical parameters with the efficacy of tofacitinib treatment are scarce. Prior, analyses based on P123 and LTE Tofacitinib data have shown: a) early achievement of clinical disease control seems to determine longer term treatment effect with Tofacitinib in MTX-naïve patients; b) Tofacitinib treatment response at 6m may be higher for patients with higher disease activity at baseline based on CRP levels particularly for those with inadequate response to biologic DMARDs.^{13,14} These results point out the need for more research and further investigation in order to help identify biomarkers that can predict response to tofacitinib treatment in patients with RA.

The impact of RA on work can be profound since permanent work disability (inability to continue working), is common among patients with RA.¹⁵ In addition to the consequences for the patient, such as a decreased quality of life, work disability also leads to high costs. It is estimated that approximately one-third of the total cost for patients with RA is caused by production losses.¹⁶ This implies that at-work productivity loss is an important concern, since work hours are not only lost incidentally through sick leave, but also more structurally and profoundly by at-work productivity loss. As so far data on the impact of Tofacitinib on work productivity are still limited, this study will assess the effect Tofacitinib on work productivity and non-work activities.

8. RESEARCH QUESTION AND OBJECTIVES

The primary objective of this study is to identify clinical and/or biochemical factors that predict achievement of remission or LDA in patients with RA treated with tofacitinib.

The secondary objectives of the study are:

- To describe the treatment patterns of RA patients prescribed tofacitinib in a real-world setting;
- Assess the effect of treatment on patient quality of life and physical function;
- Estimate resource utilization and costs in patients with rheumatoid arthritis (RA) treated with tofacitinib in Greece.

Only a subset of non-serious AEs, collected in the study database, will be reported to Pfizer Safety. This subset will consist of the non-serious AEs that are actively sought due to Pfizer's intention to align with those areas identified as important missing information or a potential risk in the product risk management plan (RMP) of Tofacitinib.

8.1. Endpoints

8.1.1. Primary Endpoint:

- a. Identify baseline characteristics that predict remission or LDA at month 6 of treatment, assessed by DAS28-4 (CRP) <2.6 and DAS28-4 (CRP) <3.2, respectively.

8.1.2. Key Secondary Endpoints:

- a. Identify baseline characteristics that predict remission or LDA at month 12 of treatment, assessed by DAS28-4 (CRP) <2.6 and DAS28-4 (CRP) <3.2 , respectively.
- b. Change from Baseline in DAS 28-4 (ESR) and DAS 28-4 (CRP) at any time point.
- c. Change from Baseline in HAQ-DI at any time point.
- d. Rate of remission at any other time point, as assessed by: SDAI ≤3.3 ; CDAI ≤2.8 ; DAS 28-4 (ESR) <2.6 and DAS28-4 (CRP) <2.6 .
- e. Rate of LDA at any other time point, as assessed by: SDAI ≤11 ; CDAI ≤10 ; DAS 28-4 (ESR) <3.2 and DAS28-4 (CRP) <3.2 .
- f. Percentage HAQ-DI responders (decrease of at least 0.22) at any time point.
- g. Change from Baseline in EuroQol EQ-5D Health State Profile at any time point.
- h. Change from Baseline in FACIT-Fatigue scale at any time point.
- i. Change from baseline in duration of morning stiffness at any time point.
- j. Change from Baseline in Work Productivity and Activity Impairment (WPAI) Questionnaire at any time point.
- k. Assess the use of healthcare resources and costs in patients with RA treated with tofacitinib in Greece.
- l. Patients satisfaction with treatment at baseline and month 12.
- m. Describe the treatment patterns of RA patients prescribed tofacitinib in a real-world setting.

9. RESEARCH METHODS

9.1. Study Design

[figure not shown]
This is a 24-month, prospective, non-interventional, multi-center study with primary aim to identify clinical and/or biochemical factors that predict achievement of remission or LDA in patients with RA treated with tofacitinib in Greece. Eligible subjects will be followed from the date of first tofacitinib prescription until study end, death, or discontinuation, or loss to follow-up (whichever comes first) for the occurrence of the endpoints of interest.

In this study, the medicinal product(s) are prescribed in the usual manner in accordance with the terms of the marketing authorisation.

The assignment of the patient to a particular therapeutic strategy is not decided in advance by this protocol, but falls within current practice and the prescription of the medicine should be clearly separated from the decision to include the patient in the study.

No additional diagnostic or monitoring procedures will be applied to the patients and follow-up visits are captured as part of normal medical practice. Epidemiological methods will be used for the analysis of collected data.

Figure 1. Study Design

9.2. Setting

The planned recruitment period is 12 months. With planned observation duration of 12 months per patient, the entire study would thus last for 24 months at maximum. The study is to start in May 2020 and will be ended in May 2022. Overall, about 200 patients in 19 centres are to be included in this non-interventional study. A patient will be followed up until the end of the planned study duration, regardless of any missing intermediate visits, as well as treatment changes during the course of follow-up.

9.2.1. Inclusion Criteria

Subject eligibility should be reviewed and documented by an appropriately qualified member of the investigator's study team before subjects are included in the study.

Evidence of a personally signed and dated informed consent document indicating that the subject (or a legally acceptable representative) has been informed of all pertinent aspects of the study is a requirement for inclusion into this study.

Subjects must meet all of the following inclusion criteria to be eligible for inclusion in the study:

Adult subjects with moderately to severely active rheumatoid arthritis who start treatment with tofacitinib in usual clinical practice conditions in compliance with the label.

1. Patients aged ≥ 18 years.
2. Confirmed Diagnosis of Rheumatoid Arthritis by rheumatologist.

3. Patients with moderate to severe RA diagnosed according to local practice who have already been started on treatment with tofacitinib, for at most seven working days.
4. Patients eligible for tofacitinib treatment according to current approved Summary of Product Characteristics (SmPC).
5. Evidence of a personally signed and dated informed consent document indicating that the patient (or a legally acceptable representative) has been informed of all pertinent aspects of the study.

9.2.2. Exclusion Criteria

Patients meeting any of the following criteria will not be included in the study:

1. Exclusion Criteria according to the Xeljanz® SmPC.
2. Contraindications to Xeljanz® according to SmPC.
3. Hypersensitivity to the active substance (tofacitinib) or to any of the excipients.
4. Active tuberculosis (TB), serious infections, such as sepsis, or opportunistic infections.
5. Receipt of any investigational drug within 3 months before study inclusion as well as currently not participating in an interventional clinical trial.
6. Subjects who have received any previous treatment with tofacitinib or other JAK inhibitors.
7. Subjects who are investigational site staff members or subjects who are Pfizer employees directly involved in the conduct of the trial.

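### Exclusion criterion 5 has a reversed second clause: not being in an interventional trial counts towards exclusion, and being in one is never itself an exclusion

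*Protocol*

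**What the plan says.** The exclusion list in Protocol Section 9.2.2 opens with the rule "Patients meeting any of the following criteria will not be included in the study". Item 5 of that list is "Receipt of any investigational drug within 3 months before study inclusion as well as currently not participating in an interventional clinical trial".

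The target population is set just before it. Section 9.2.1 describes adults with active disease "who start treatment with tofacitinib in usual clinical practice conditions in compliance with the label", and Section 9.2 gives the scale: "Overall, about 200 patients in 19 centres are to be included in this non-interventional study".

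No other text in the protocol or SAP states a rule on taking part in another trial at the same time. The inclusion criteria are silent on it, and SAP Section 2.2 does not restate eligibility. The only eligibility change in the amendment log (Protocol Section 5) is "Clarified Inclusion criterion 3"; it lists no change to exclusion criterion 5.

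**The concern.** Under the opening rule, each item should describe a patient the study does not want. The second half of item 5 describes the patient it does want, namely someone who is not in an interventional trial. Read literally, the sentence either turns away ordinary-care patients or fails to turn away patients in a concurrent trial.

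Eligibility has to be reviewed and documented for every subject (Section 9.2.1), consecutive patients enter if they satisfy all the criteria (Section 9.4.1), and monitors check adherence to the protocol (Section 9.8). Nineteen centres would therefore be documenting compliance with a sentence that does not say what it appears to mean, and they may resolve it differently.

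What is at stake is mainly the descriptive results. A concurrent interventional trial can set visits, tests and co-treatment. Healthcare resource use and treatment patterns are both secondary endpoints (Section 8.1.2, items k and m). Resource use is measured by counting specialist visits, diagnostic tests and hospitalisations (SAP Section 6.3.1). Concomitant treatment is also a candidate predictor in the logistic models (SAP Section 6.4).

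**Working it through.** The documents give no figure to reproduce and no arithmetic applies. The check is one of logic.

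**Definitions.** Let A be receipt of an investigational drug within 3 months, and B be current participation in an interventional trial. Item 5 combines A with not-B, joined by *as well as*. That joining phrase can be taken in two ways:

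- *Either clause excludes*: A or not-B. This is the more natural reading in a list of exclusions.
- *Both clauses are needed*: A and not-B.

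The last column shows the evident intent, A or B.

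| A: recent investigational drug | B: in a trial now | A or not-B | A and not-B | Intent: A or B |
|---|---|---|---|---|
| No | No | Excluded | Not excluded | Not excluded |
| Yes | No | Excluded | Excluded | Excluded |
| No | Yes | Not excluded | Not excluded | Excluded |
| Yes | Yes | Excluded, through A | Not excluded | Excluded |

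**Row 1** is the routine-care patient of Sections 9.2 and 9.2.1. The natural reading excludes this patient, which contradicts the target population.

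**Row 3** is a trial participant with no recent investigational drug, for example in a strategy or device trial, or enrolled but not yet dosed. Item 5 excludes this patient on neither reading.

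**Row 4** is a recently dosed drug-trial participant. The first clause, which is not inverted, still catches this patient on the natural reading. Only the joint reading lets this patient through.

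On both literal readings, B never triggers exclusion and not-B counts towards it. Neither reading reproduces the last column.

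**Does a later step remove such a patient?** The Full Analysis Set needs one dose and one set of post-baseline measurements; the Safety Analysis Set needs one dose (Protocol Section 9.7.1; SAP Sections 5.1 and 5.2). Neither refers to eligibility, and no per-protocol set is defined. A co-enrolled patient who met these definitions would therefore stay in the efficacy and resource-use analyses, which use the Full Analysis Set (SAP Sections 8.2.3 and 8.2.4.1). The same patient would stay in the treatment-pattern summaries, which are placed under the safety analyses (SAP Section 8.2.2).

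**The case against.** The strongest reply is that the intent is plain. This is a non-interventional study of consecutive patients starting tofacitinib in usual practice, and the second clause is evidently an entry requirement put in the wrong list. Most sites would read it that way. That stands, and it limits the consequence, but it does not make the sentence correct.

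A reader might infer that the study would exclude all of its roughly 200 patients, or admit every patient who is in another trial. The documents do not support either as a forecast. Both are outcomes of literal logic, the first would defeat the study outright, and no count of co-enrolled candidates is given.

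A reader might also infer that patients now taking an investigational drug in a trial would be admitted. On the natural reading they would not, because the first clause excludes anyone given such a drug within 3 months.

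The usual-practice wording of Sections 9.1 and 9.2.1 gives partial protection: a patient whose tofacitinib was assigned by another trial would be hard to square with it. That narrows the gap but does not close it, since a concurrent trial may govern something other than tofacitinib. Nor can Section 9.1 be read as a ban on co-enrolment. Its statement, "The assignment of the patient to a particular therapeutic strategy is not decided in advance by this protocol, but falls within current practice", concerns this study's own protocol and is silent on other trials.

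Finally, the content of any eDCT eligibility check is not in the documents, so nothing shows that the error is repeated there.

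**Conclusion.** The point holds as a drafting error in an operative eligibility rule. The second clause of criterion 5 has the wrong polarity under the list's opening rule, and nothing elsewhere in the documents corrects it. This conclusion rests on the text alone.

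The size of the effect cannot be stated, because the documents do not say how many candidates are in other trials or how sites would read the sentence. The realistic risk is inconsistent application across 19 centres and an occasional co-enrolled patient retained in the analysis sets. It assumes that at least one site departs from the evident intent. A claim that the results are contaminated would go beyond the documents. The endpoint definitions, the sample-size calculation in Section 9.5 and the specified models are unaffected.

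**What to change.** Reconcile criterion 5 with the opening rule of the list by splitting it into two separate exclusions:

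- **5a.** Any investigational drug received in the 3 months before inclusion.
- **5b.** Current enrolment in an interventional clinical trial.

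Confirm, as a precaution, that any eligibility check in the eDCT uses the same polarity, so that *yes* to either item means excluded.

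The cost is one line in a protocol amendment and a check of the eDCT. It restores the evident intent, does not narrow the intended population and needs no change to the SAP.

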9.3. Variables

Variable	Role	Data source(s)	Operational definition
RA-treatment with Tofacitinib and/or other DMARDs – date of initiation	Exposure, Potential confounder, subgroup identifier	Case records and electronic Case Report Form (eDCT)	Details will be provided in Statistical Analysis Plan
RA treatment with Tofacitinib and/or other DMARDs – dose	Exposure, Potential confounder, subgroup identifier	Case records and eDCT	Details will be provided in Statistical Analysis Plan
RA treatment with Tofacitinib and/or other DMARDs - tolerability	Potential confounder, subgroup identifier	Case records and eDCT	Details will be provided in Statistical Analysis Plan
RA treatment with Tofacitinib and/or other DMARDs – route of administration	Potential confounder, subgroup identifier	Case records and eDCT	Details will be provided in Statistical Analysis Plan
Time of tofacitinib initiation	Exposure	Case records/eDCT	Details will be provided in Statistical Analysis Plan

Tofacitinib citrate
A3921342 NON-INTERVENTIONAL STUDY PROTOCOL
Version 2.0, 14 January 2020

Variable	Role	Data source(s)	Operational definition
Age	Baseline characteristic, potential confounder, sub-group identifier	Case records/eDCT	Details will be provided in Statistical Analysis Plan
Gender	Baseline characteristic, potential confounder, sub-group identifier	Case records/eDCT	Details will be provided in Statistical Analysis Plan
Height	Baseline characteristic, potential confounder, sub-group identifier	Case records/eDCT	Details will be provided in Statistical Analysis Plan
Weight	Baseline characteristic, potential confounder, sub-group identifier	Case records/eDCT	Details will be provided in Statistical Analysis Plan
Date of first diagnosis of RA	Baseline characteristic, potential confounder, sub-group identifier	Case records/eDCT	Details will be provided in Statistical Analysis Plan
Anti-citrullinated protein antibodies (ACPA)	Baseline characteristic, potential confounder, sub-group identifier	Case records/eDCT	Details will be provided in Statistical Analysis Plan
RF	Baseline characteristic, potential confounder, sub-group identifier	Case records/eDCT	Details will be provided in Statistical Analysis Plan
Structural damage	Baseline characteristic, potential confounder, sub-group identifier	Case records/eDCT	Details will be provided in Statistical Analysis Plan
RA Extra-articular manifestations	Baseline characteristic, potential confounder, sub-group identifier	Case records/eDCT	Details will be provided in Statistical Analysis Plan
Smoking history and current smoking status	Baseline characteristic, potential confounder, sub-group identifier	Case records/eDCT	Details will be provided in Statistical Analysis Plan
Alcohol intake	Baseline characteristic, potential confounder, sub-group identifier	Case records/eDCT	Details will be provided in Statistical Analysis Plan
Vaccination status	Baseline characteristic, potential confounder, sub-group identifier	Case records/eDCT	Details will be provided in Statistical Analysis Plan
Tuberculosis status	Baseline characteristic, potential confounder, sub-group identifier	Case records/eDCT	Details will be provided in Statistical Analysis Plan
Hepatitis status	Baseline characteristic, potential confounder, sub-group identifier	Case records/eDCT	Details will be provided in Statistical Analysis Plan
Co-morbidities	Baseline characteristic, potential confounder, sub-group identifier	Case records/eDCT	Details will be provided in Statistical Analysis Plan
Co-medication	Potential confounder, sub-group identifier	Case records/eDCT	Details will be provided in Statistical Analysis Plan
Prior medication for RA	Potential confounder, sub-group identifier	Case records/eDCT	Details will be provided in Statistical Analysis Plan
Concomitant medications for RA (steroids; NSAIDs, csDMARDs, bDMARDs)	Potential confounder, sub-group identifier	Case records/eDCT	Details will be provided in Statistical Analysis Plan
Erythrocyte Sedimentation Rate (ESR)	Baseline characteristics and outcome variable	Case records/eDCT	Details will be provided in Statistical Analysis Plan
C-Reactive Protein (CRP)	Baseline characteristics and outcome variable	Case records/eDCT	Details will be provided in Statistical Analysis Plan
Patient's global assessment of arthritis	Baseline and outcome variable	Case records/eDCT	Details will be provided in Statistical Analysis Plan

PFIZER CONFIDENTIAL

Variable	Role	Data source(s)	Operational definition
Physician's global assessment of arthritis	Baseline and outcome variable	Case records/eDCT	Details will be provided in Statistical Analysis Plan
EuroQol EQ-5D Health State Profile	Baseline and Outcome	Case records/eDCT	Details will be provided in Statistical Analysis Plan
Health Assessment Questionnaire – Disability Index (HAQ-DI)	Baseline and Outcome	Case records/eDCT	Details will be provided in Statistical Analysis Plan
Tender (28) joint count	Baseline and Outcome	Case records/eDCT	Details will be provided in Statistical Analysis Plan
Swollen (28) joint count	Baseline and Outcome	Case records/eDCT	Details will be provided in Statistical Analysis Plan
Functional Assessment of Chronic Illness Therapy (FACIT) Questionnaire	Baseline and Outcome	Case records/eDCT	Details will be provided in Statistical Analysis Plan
Work Productivity and Activity Impairment (WPAI) Questionnaire	Baseline and Outcome	Case records/eDCT	Details will be provided in Statistical Analysis Plan
Morning Stiffness	Baseline and Outcome	Case records/eDCT	Details will be provided in Statistical Analysis Plan
Patient Assessment of Arthritis Pain	Baseline and Outcome	Case records/eDCT	Details will be provided in Statistical Analysis Plan
Patients satisfaction with drug treatment	Baseline and Outcome	Case records/eDCT	Details will be provided in Statistical Analysis Plan
Medical visits	Outcome	Case records/eDCT	Details will be provided in Statistical Analysis Plan
Diagnostic tests	Outcome	Case records/eDCT	Details will be provided in Statistical Analysis Plan
Hospitalizations	Outcome	Case records/eDCT	Details will be provided in Statistical Analysis Plan
Educational level	Baseline, sub-group identifier	Case records/eDCT	Details will be provided in Statistical Analysis Plan
Working status	Baseline and outcome, sub-group identifier	Case records/eDCT	Details will be provided in Statistical Analysis Plan

